A power analysis was conducted for the post-operative pain outcomes; being a novel intervention, opioid taper outcomes were not considered. Estimated group means, variances, and effect-size were drawn from the literature.^{41,42} The sample size estimate was derived for the primary outcome variable, chronic pain severity, using an expected baseline mean of 4.82 (Effect size: 0.33). Based on estimates obtained, a sample size of 75 participants provides 80% power to detect a pre-post improvement in pain severity (14.5%), depression (21.3%), anxiety (24.3%), and catastrophizing (29.5%), statistically significant at alpha of 0.05. Being a novel intervention, the analysis for chronic post-surgical pain will be considered exploratory and used to obtain effect size estimates. We anticipate a low attrition rate (10%) and will over-recruit 16 additional participants (total 83 subjects per group) to retain adequate power.

2. Key Inclusion Criteria:

[figure not shown]

Figure 1. Predictive factors of CPSP following TKA

1. Males and females, age > 21 years
2. Chronic non-malignant pain of at least 3 months duration
3. Morphine equivalent daily dose (MEDD) > 50 milligrams for at least 3 months
4. Able to enroll at least 4 weeks prior to planned surgery
5. Able to speak, read and comprehend in English at the 6th grade or higher proficiency

Participants will be selected so as to represent the gender, ethnicity, and age of the patient population of individuals seeking TKA in greater Philadelphia area, thus the sample is expected to be 50% women, 55% white, 35% African-American, 6-8% Latino, and 2-4% other or multiracial, and on average 67 years of age. No restrictions on gender or ethnicity will be applied. Because total knee arthroplasty surgery is uncommon in children, individuals under the age of 21 will not be included in this proposed study.

3. Key Exclusion Criteria:

1. Pain of malignant origin
2. Current or past history of opioid use disorder (including those on medication-assisted therapy)
3. Revision of TKA
4. Comorbid CNS disease such as dementia, HIV, psychosis, poorly controlled bipolar disorder or any condition interfering with informed consent

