Pain of malignant origin is likely to worsen with disease progression over time, thus the efficacy of the intervention on pain outcomes would be limited. Similarly, opioid use in patients with opioid use disorder is motivated by factors other than pain, thus opioid use outcomes would be spurious if these patients were included in the analysis. Finally, surgical outcomes for patients undergoing a revision of their TKA have poorer pain and functional outcomes, introducing known variance to the efficacy of the intervention; excluding them from the sample preserves homogeneity as required for a small pilot study.

4. Subject Recruitment and Screening:

Participants will be recruited from those preparing to undergo total knee arthroplasty (TKA) surgery at the large and nationally-renowned Department of Orthopedic Surgery at the Penn Presbyterian Medical Center. The Center performs approximately 1100 major TKAs per year with an estimated 20-30% of patients who have been taking opioids regularly for at least 3 months for the treatment of a chronic nonmalignant pain condition.

The EHR of all patients scheduled for TKA at least 5 weeks in the future will be examined to identify those meeting inclusion criteria. Eligibility will be reviewed by Co-I [name]; those eligible will be contacted by the study coordinator to inform them about the study. Those who express interest will be scheduled for a screening visit during which informed consent will be obtained in a Center private room.

If a patient assigned to standard treatment requests the enhanced treatment, he or she will be removed from the study.

5. Early Withdrawal of Subjects:

Subjects may be withdrawn from the study prior the expected completion of the project if there are concerns about the safety of the subject, failure of subject to return for visits, failure to locate the subject and if subjects withdraw their consent. Concerns about safety include feelings of extreme anxiety or depression which will be evaluated by co-PI [name].

Subjects are also informed via the informed consent process that they are free to leave the study at any time, and that withdrawal will not interfere with their future care.

6. Vulnerable Populations:

Children, pregnant women, fetuses, neonates, or prisoners are not included in this research study.

7. Populations vulnerable to undue influence or coercion:

The population from which the sample will be recruited are not vulnerable to coercion or undue influence.

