STUDY DESIGN:

A randomized clinical trial is proposed to evaluate the efficacy of the novel computer-assisted preoperative CBT/opioid sparing intervention to affect acute and chronic post-operative pain outcomes. Specifically, 150 male and female patients meeting study inclusion criteria and preparing to undergo TKA at the Penn Presbyterian Medical Center will be randomized to either receive the computer-assisted preoperative CBT intervention (n=75) or treatment-as-usual (control, n=75). The effectiveness of the intervention to address the preoperative risk factors for CPSP will be evaluated by comparing pain severity, opioid use, symptoms of depression, anxiety and pain catastrophizing before and following the 4-week pre-surgical period and compared within and across subjects. Post-operative pain severity will be abstracted from the electronic health record (EHR) and compared to post-operative pain severity ratings between the intervention and control groups. Similarly, group differences will be inspected for rates of CPSP at 3- and 6-months following surgery. In addition, due to the novelty of the CBT/opioid sparing intervention, brief (15-20min) qualitative interviews will be conducted with the participants who received it during the study visit immediately prior to surgery, to assess patient utilization, and satisfaction with the program in general, and the opioid taper component specifically; adherence is tracked by the PAINTrainer. Participants will be prompted to comment on the perceived ease of use, burden, helpfulness and quality of the CBT intervention.

A randomized clinical trial was designed because it provides the highest level of evidence and lowest risk for bias. The methods employed are predominantly quantitative, although a qualitative survey approach is used to assess subject satisfaction with the intervention. The project is designed, staffed and budgeted to be completed in 24 months. In consultation with consultants, [name] will train the study coordinator coach on delivering the opioid taper intervention during months 1-3, during which time study start-up activities will take place. Enrollment will begin month 3; at a rate of 12-13 enrollments per month, we anticipate having enrolled 166 subjects (n=150, assuming 10% attrition) by study month 15, providing adequate time for 3- and 6-month follow up, and dissemination activities.

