The Study Coordinator/Coach, TBH, will devote 12 calendar months effort to the study over both years of the project. This individual will come to the project with experience in coordinating human subject clinical research studies and be responsible for enrolling subjects, scheduling study visits, all aspects of data collection, entering study data into REDCap, and engaging in ongoing communication with IRB, study setting and U Penn School of Medicine and Nursing, Department of Anesthesiology and Department of Orthopaedic Surgery. In addition, this individual will receive directed training and monitoring from Co-PI [name] to oversee delivery of the CBT and opioid tapering MI intervention. In this role, this individual will serve as a "coach" to the subjects, contacting them on a weekly basis prior to surgery, educating and motivating them to engage in preoperative opioid reduction.

Participants will be recruited from the nationally renowned Department of Orthopaedic Surgery at PPMC. Center surgeons perform approximately 1800 major TKAs per year, an estimated 20-30% of whom have been taking opioids for at least 3 months for the treatment of a chronic nonmalignant pain condition, resulting in a recruitment pool of 30 to 45 patients per month, providing an adequate source of the necessary 12-13 enrollments per month.

In addition, the facilities and resources are adequate to safely conduct the study. Situated within the Department of Psychiatry is the Center for Studies on Addiction (CSA), where Co-Principal Investigator [name] holds an appointment. A primary mission of the CSA is to continue to advance the cutting edge of knowledge on the nature of addiction and the best ways to treat this disorder. The CSA has, for the past 40 years, been an important

national and international resource for addictions research. The PI ([name]) has conducted large-scale studies on pain and opioid use disorders and suicide and has an established relationship at the primary recruitment site.

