[name] has private locking office in the Perelman School of Medicine and shared office space in the primary recruitment site, PPMC. At both facilities, his office space is equipped with locked filing cabinets, bookshelves, desk, minimum 4 GHz computer with HP printer, Windows XP service pack 3 operating system, Microsoft Office Professional (Word, Excel, PowerPoint, Access), SPSS or SAS statistical analysis software, and e-mail and internet access. He enjoys full access to the centralized Department of Orthopaedic Surgery database through which patient randomization and data collection will be done.

Study Surgeons [name] and [name] practice in the Department of Orthopaedics (Penn Orthopaedics) which boast a talented and specialized interdisciplinary team of health care providers dedicated to a whole-body approach to diagnosing and treating joint pain. They complete thousands of joint procedures a year (approximately 1100 primary TKAs and 500 TKA revisions), and provide services in sports medicine, cartilage repair, neuro-orthopedics, orthopaedic oncology, and trauma and fracture repair.

The Department of Orthopaedics provides the latest diagnostic techniques and the most advanced surgical and non-surgical options for a range of disorders, injuries and pain found in joints, muscles or bones. Penn Orthopaedics has 49 exam rooms, 4 Operating Rooms for Outpatient Procedures and 2 floors of Physical and Occupational Therapy at Penn Medicine University City. It brings together Penn clinicians from numerous specialties, including orthopaedics, rheumatology, physical medicine and rehabilitation, pain medicine and musculoskeletal radiology. This team-based model of care creates a seamless, integrated patient experience and the most efficient process towards an accurate diagnosis and appropriate treatment plan. Drs. [name] and [name] each have their own 100 square feet offices with computers, printers, internet access and standard furniture.

In addition to clinical space, to support research activities, the Department of Orthopaedic Surgery provides space and resources for Clinical Research staff (up to 10 full time coordinators) associated with these studies. The

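### The recruitment pool of 30-45 patients per month rests on 1800 knee replacements a year, but the protocol elsewhere gives 1100; with 1100 it is 18-28 before dose and other eligibility losses, and accrual by month 15 is not demonstrated

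*Combined protocol and SAP*

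**What the plan says.** Three places give an annual volume of total knee arthroplasties (TKAs).

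- **Resources Necessary for Human Research Protection, recruitment paragraph:** the volume is given as "Center surgeons perform approximately 1800 major TKAs per year". The share of these patients on long-term opioids is put at 20-30%, and the paragraph presents the two figures as "resulting in a recruitment pool of 30 to 45 patients per month". The pool is then described as adequate for the 12-13 enrolments needed each month.
- **Characteristics of the Study Population, item 4 (Subject Recruitment and Screening):** the volume is given as "The Center performs approximately 1100 major TKAs per year". The opioid share is again put at 20-30%.
- **Resources section, paragraph on the study surgeons:** "approximately 1100 primary TKAs and 500 TKA revisions".

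The eligibility criteria exclude revision procedures and patients with current or past opioid use disorder. They also require "Morphine equivalent daily dose (MEDD) > 50 milligrams for at least 3 months" and enrolment at least 4 weeks before surgery.

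On timing, Study Design starts enrolment in month 3 and says "we anticipate having enrolled 166 subjects (n=150, assuming 10% attrition) by study month 15"; the Resources section repeats this. The project is planned for 24 months, and each subject takes part for about seven.

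**The concern.** The statement that accrual is adequate depends on one input, the annual TKA volume, and the protocol gives that input two values that differ by a factor of 1.6. The pool estimate uses the larger. The smaller appears twice, once for the same Center with the same opioid share and once explicitly for primary procedures, the type that the exclusion criteria leave in.

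The 20-30% share also counts opioid users of at least 3 months at any dose. The dose threshold, the opioid use disorder exclusion, the lead time before surgery and refusal are not taken off. Refusal is not a trivial item: the intervention takes about nine hours and participation is unpaid.

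At stake is the timetable. Enrolment to month 15 plus about seven months of participation puts the last follow-up near month 22 of 24. Slower accrual would mean a smaller sample than the 150 planned, or 6-month follow-up that runs past the end of the project.

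**Working it through.** **Inputs.** Annual TKA volume: 1800 (Resources), 1100 (Subject Recruitment and Screening), 1100 primary + 500 revision = 1600 (Resources, study surgeons). Opioid share: 20-30%. Required rate: 12-13 per month. Target: 166, from month 3 to month 15, which is 13 months if both are counted.

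**Formula.** Pool per month = annual volume × opioid share / 12.

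**Step 1. Reproduce the stated pool.** 1800 × 0.20 / 12 = 30.0 and 1800 × 0.30 / 12 = 45.0. This matches exactly, so the pool does rest on 1800.

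**Step 2. Repeat with the other volumes.** Required capture is the enrolment rate divided by the pool, from 12 / upper pool to 13 / lower pool.

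| Annual volume | Pool per month | Required capture |
|---|---|---|
| 1800 | 30.0-45.0 | 12/45 = 27% to 13/30 = 43% |
| 1600 (includes excluded revisions) | 26.7-40.0 | 12/40 = 30% to 13/26.7 = 49% |
| 1100 | 18.3-27.5 | 12/27.5 = 44% to 13/18.3 = 71% |

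Even adding the excluded revisions does not reach 1800.

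**Step 3. Accrual if uptake does not change.** For a fixed opioid share and a fixed uptake, the rate is proportional to volume. The factor is 1100/1800 = 0.611.

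- Rate: 12 × 0.611 = 7.3 and 13 × 0.611 = 7.9 per month.
- Time to 166: 166/7.94 = 20.9 and 166/7.33 = 22.6 months, against 166/12.8 = about 13 as planned.
- Enrolled in 13 months: 13 × 7.33 = 95 to 13 × 7.94 = 103. After 10% attrition, that is about 86 to 93, against 150.
- Starting in month 3, the last enrolment falls in about month 23 to 25. Adding about seven months of participation gives month 30 to 32.

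**Step 4. Room for the filters not applied.** The target needs 166/13 = 12.8 per month. On the 1100 figure, even if every eligible patient consented, the pool would fall below this if fewer than 12.8/27.5 = 46% (opioid share 30%) or 12.8/18.3 = 70% (opioid share 20%) of opioid users met the remaining criteria. The documents give neither that share nor a consent rate. As assumptions only:

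| Assumed share meeting the remaining criteria | Pool per month (1100) | Capture needed for 12.8 |
|---|---|---|
| 75% | 13.8-20.6 | 62-93% |
| 50% | 9.2-13.8 | 93-139% |
| 25% | 4.6-6.9 | above 100% throughout |

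**Step 5. Slack in the timetable.** 12-13 per month yields 144-156 in 12 months and 156-169 in 13. So 166 needs a rate near the top of the range with months 3 and 15 both counted.

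**The case against.** Several points on the other side stand.

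- **The documents do not say which volume is right.** A reader might infer that 18-28 per month is the true pool of eligible patients. Neither passage calls the 1100 eligible. The recruitment section calls them major, the same word used for the 1800; only the surgeons' paragraph says primary, and its wording leaves open whether the count belongs to the named surgeons or to the department. The 1100 figure is better supported, but not proven.
- **The volume error does not by itself defeat the target.** A reader might infer that 166 enrolments are out of reach. On the 1100 figure the pool still exceeds 12-13 per month before further losses. A shortfall needs a low share meeting the other criteria, or low consent, and the documents quantify neither.
- **A wider accrual range would be wrong.** Pairing the highest implied uptake with the largest 1100-based pool, and the lowest with the smallest, suggests about 14 to 34 months. This mixes opioid shares: the 43% uptake assumes a 20% share and the 27% uptake assumes 30%. With the share held fixed it cancels, leaving 21-23 months.
- **The sample size does not depend on the pool.** It comes from the power calculation under Target Population and Accrual. The protocol calls the study a small pilot aimed at effect size estimates, and no estimand, endpoint or analysis changes.

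What these points do not remove is the contradiction between the volumes, or the fact that the adequacy statement uses the figure that nothing else in the protocol supports.

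**Conclusion.** The point holds as a feasibility finding. The stated pool of 30-45 per month depends on a volume that the protocol contradicts elsewhere. On the better supported 1100, the pool is 18-28 per month, 39% smaller (1 − 1100/1800), and the required capture rises from 27-43% to 44-71% before any loss to dose, opioid use disorder, scheduling or consent. These figures use only the documents' numbers.

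The 21-23 months of accrual, and the 95-103 enrolled by month 15, assume in addition that uptake stays at the level implied by the stated pool. The 75%, 50% and 25% rows are illustrations. The supportable conclusion is that enrolment of 166 by month 15 is not demonstrated, not that it is impossible. The consequence is for the timetable and the sample delivered, not for the validity of the analysis.

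**What to change.** 1. Reconcile the annual volumes in Subject Recruitment and Screening and in the two paragraphs of the Resources section, stating whether each counts primary procedures only and whether it covers the Center, the department or the study surgeons.
2. Restate the pool from the reconciled figure: 18-28 per month if 1100 is confirmed.
3. Use the record screen already planned for recruitment to count, over a recent period, patients who meet all criteria, including the dose threshold, the opioid use disorder exclusion and the lead time before surgery.
4. Restate the expected monthly rate and the last-enrolment month from that count with an explicit consent assumption, and check that the 6-month follow-up still fits within 24 months.

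The cost is a text correction and one count from records the team already intends to examine. The downside is that the stated feasibility becomes less favourable.

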[name] has private locking office in the Perelman School of Medicine and shared office space in the primary recruitment site, PPMC. At both facilities, his office space is equipped with locked filing cabinets, bookshelves, desk, minimum 4 GHz computer with HP printer, Windows XP service pack 3 operating system, Microsoft Office Professional (Word, Excel, PowerPoint, Access), SPSS or SAS statistical analysis software, and e-mail and internet access. He enjoys full access to the centralized Department of Orthopaedic Surgery database through which patient randomization and data collection will be done.

Study Surgeons [name] and [name] practice in the Department of Orthopaedics (Penn Orthopaedics) which boast a talented and specialized interdisciplinary team of health care providers dedicated to a whole-body approach to diagnosing and treating joint pain. They complete thousands of joint procedures a year (approximately 1100 primary TKAs and 500 TKA revisions), and provide services in sports medicine, cartilage repair, neuro-orthopedics, orthopaedic oncology, and trauma and fracture repair.

The Department of Orthopaedics provides the latest diagnostic techniques and the most advanced surgical and non-surgical options for a range of disorders, injuries and pain found in joints, muscles or bones. Penn Orthopaedics has 49 exam rooms, 4 Operating Rooms for Outpatient Procedures and 2 floors of Physical and Occupational Therapy at Penn Medicine University City. It brings together Penn clinicians from numerous specialties, including orthopaedics, rheumatology, physical medicine and rehabilitation, pain medicine and musculoskeletal radiology. This team-based model of care creates a seamless, integrated patient experience and the most efficient process towards an accurate diagnosis and appropriate treatment plan. Drs. [name] and [name] each have their own 100 square feet offices with computers, printers, internet access and standard furniture.

In addition to clinical space, to support research activities, the Department of Orthopaedic Surgery provides space and resources for Clinical Research staff (up to 10 full time coordinators) associated with these studies. The

space is located in the department where we have 600 square feet of dedicated space, eleven PCs and eleven desks as well as storage for research binders and other confidential information. Electronic research files are stored on UPenn Health System secured servers behind the UPenn Health System firewall and are additionally protected through the use of limited access folders on the servers. Clinical data is maintained in PennChart which is a Penn-specific image of EPIC Electronic Medical Records Software (Epic Systems Corporation, Madison, Wisconsin).

The project is designed, staffed and budgeted to be successfully completed in 24 months. In consultation with Drs. [name] and [name], [name] will train the study coordinator coach on delivering the opioid taper MI intervention during months 1-3, during which time study start-up activities will take place. Enrollment will begin month 3; at a rate of 12-13 enrollments per month, we anticipate having enrolled 166 subjects (n=150, assuming 10% attrition) by study month 15, providing adequate time for 3- and 6-month follow up, and dissemination activities.

REFERENCES

1. http://aaos-annualmeeting-presskit.org/2018/research-news/sloan_tjr/
2. <https://www.ncbi.nlm.nih.gov/pubmed/17403800>
